**Table 2**

Attribution	SAE				AE		
	Grade 1, 2 & 3		Grade 4 and 5		Grade 3	Grade 4	
	Expected	Unexpected	Expected	Unexpected	Unexpected	Expected	Unexpected
Unrelated Unlikely	IRB  and DSMC  - Routine Review 	IRB  and DSMC  - Routine Review 	IRB  - Routine Review   DSMC  - Within 5 calendar days	IRB  - Routine Review   DSMC  - Within 5 calendar days	DSMC  - Routine Review 	DSMC  - Within 5 calendar days	DSMC  - Within 5 calendar days
Possible Probable Definite		IRB  and DSMC  - Within 5 calendar days		IRB  and DSMC  - Within 5 calendar days			

1. Guidance on Adverse Event Reporting to the IRB is available online at MCW IRB Policies and Procedures.
2. For expedited DSMC reporting, study coordinator/research nurse must notify the DSMC via email including the subject ID, date of event, grade, relatedness, expectedness, and a short narrative. DSMC will review data entered into OnCore®.
3. For routine reporting, the events will be reported to IRB as part of the annual continuing progress report and the DSMC will review data entered into OnCore® at the time of scheduled monitoring.

### 6.3 Unanticipated Problem Involving Risk to Subject or Other (UPIRSO)

The investigator and his or her team will follow the Medical College of Wisconsin policies related to unanticipated problems involving risks to subjects or others. This information may be found on the [Human Research Protection Program website](#).

## **6.4 Subject Complaints**

If a complaint is received by anyone on the study staff, it will be discussed with the study staff and will be addressed on a case-by-case basis. The PI will be notified of any complaints. Complaints will be reported to the IRB if indicated.

If the subject has questions about his or her rights as a study subject, wants to report any problems or complaints, obtain information about the study or offer input, the subject can call the Medical College of Wisconsin/Froedtert Hospital research subject advocate at [contact]. This information is provided to the subject in their consent.

A product complaint is a verbal, written or electronic expression that implies dissatisfaction regarding the identity, strength, purity, quality or stability of a drug product. Individuals who identify a potential product complaint situation should immediately contact the drug manufacturer and report the event. Whenever possible, the associated product should be maintained in accordance with the label instructions pending further guidance from a drug manufacturer representative. Product complaints in and of themselves are not reportable events. If a product complaint results in an SAE, an SAE form should be completed.

# **7 STATISTICAL CONSIDERATIONS**

## **7.1 Power Calculations**

The primary objective of this study is to demonstrate feasibility. With about 10 patients, assuming a local control rate of 85% (in line with observed local control rates in the literature in 2014, Asher et al. and 2016, Patel et al.), we will be able to estimate a 95% confidence interval with width not exceeding 0.40, that is about 47% of the assumed 85% local control rate.

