Study Intervention Description	Enrolled patients will receive SRS to all metastases followed by surgical resection of resectable metastases within one to 10 days following

	SRS. Pathologic specimens will be analyzed, and the patient will enter a standard pattern of surveillance (brain MRI every three months for two years).
Number of Subjects	Up to fifteen subjects will be enrolled in this study to attain ten completed subjects.
Estimated Time to Complete Enrollment:	Approximately two years.

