## **7.2 Methodology of comparisons between groups**

Descriptive statistics, including means, medians, and ranges will be reported wherever appropriate. For the primary hypothesis, the estimated rates of local control and its 95% confidence interval using an exact binomial method will be computed. For the secondary objectives, appropriate Kaplan Meier progression-free survival estimates will be computed.

All calculations will be performed using the SAS and the R language for statistical computing. Unless explicitly mentioned, all analysis will use a type I error rate of 0.05 and 95% confidence intervals.

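### With 10 patients and local control near 85%, the planned exact 95% interval is 0.44 to 0.53 wide at 9 or 8 controlled, not at most 0.40

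*Combined protocol and SAP*

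**What the plan says.** Section 7.1 names feasibility as the primary objective, then supports the sample size through local control alone. For about 10 patients at an assumed rate of 85%, it states that "we will be able to estimate a 95% confidence interval with width not exceeding 0.40" and adds, "that is about 47% of the assumed 85% local control rate". It names no interval method.

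Section 7.2 supplies the method. For the primary hypothesis, "the estimated rates of local control and its 95% confidence interval using an exact binomial method will be computed". It also sets the confidence level: unless stated otherwise, "all analysis will use a type I error rate of 0.05 and 95% confidence intervals".

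The Protocol Summary fixes the number of patients: "Up to fifteen subjects will be enrolled in this study to attain ten completed subjects". Section 7.3 leaves patients who do not complete follow-up out of the primary and secondary analyses, so the number analysed is the completers, about ten.

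**The concern.** An exact binomial interval from 10 patients is wide, and a bound of 0.40 near 85% looked too narrow. The wording states an upper limit on the width, not a typical value, so it fails if the likely results exceed it.

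Local control is one of the two primary objectives (Section 2.1), and the 50% feasibility criterion in Section 2.3 has no calculation behind it. The 0.40 is therefore the only precision or power figure offered for the sample size. If it is wrong, readers will expect more from the local control estimate than 10 patients can give.

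The protocol's own background figures show what is at stake. Section 1.4 cites about 50% recurrence at the resection cavity, which implies about 50% control. Section 1.6 cites local control of up to 83 to 94% at 24 months with postoperative radiosurgery. With 8 of 10 controlled, the exact interval (44% to 97%) contains both. With 9 of 10 (55.5% to 99.7%), it excludes 50% but still contains the whole 83 to 94% range.

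**Working it through.** **Inputs.** n = 10 (Section 7.1; ten completers in the Protocol Summary). Assumed rate p = 0.85 (7.1). Two-sided 95% confidence and exact binomial method (7.2). Stated bound 0.40 and relative width 47% (7.1).

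**The plan's figures.** 0.40 / 0.85 = 0.471, so the 47% follows from the 0.40. The 0.40 itself does not reproduce with the planned method.

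**Exact (Clopper-Pearson) limits.** For x controlled of n, the lower limit is the 0.025 quantile of Beta(x, n − x + 1) and the upper limit is the 0.975 quantile of Beta(x + 1, n − x). For x = n the lower limit is 0.025^(1/n) and the upper limit is 1; at 10/10 this gives 0.025^(1/10) = 0.6915. Since 85% of 10 is not a whole count, the results either side of it are 8 and 9.

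| Controlled | Exact 95% interval | Width | Probability if p = 0.85 |
|---|---|---|---|
| 10/10 | 0.692 to 1.000 | 0.308 | 0.197 |
| 9/10 | 0.555 to 0.997 | 0.443 | 0.347 |
| 8/10 | 0.444 to 0.975 | 0.531 | 0.276 |
| 7/10 | 0.348 to 0.933 | 0.586 | 0.130 |

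**Chance of meeting the bound.** Among results with any material probability, only 10/10 has a width of 0.40 or less. P(width ≤ 0.40) = 0.85^10 = 0.197, so the bound is exceeded about 80% of the time.

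**Expected width.** Sum the width times the Binomial(10, 0.85) probability over all x. The four rows above contribute 0.061 + 0.154 + 0.146 + 0.076 = 0.437. Lower counts add about 0.031, giving 0.468.

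**Relative width.** 0.4425 / 0.85 = 52% at 9/10; 0.531 / 0.85 = 62% at 8/10.

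**Other interval methods at n = 10.** Section 7.1 names no method, so alternatives were tried.

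| Method | Width at 85% (8.5/10) | Width at 9/10 | Width at 8/10 |
|---|---|---|---|
| Exact | 0.492 (interpolated) | 0.443 | 0.531 |
| Wald, untruncated | 0.443 | 0.372 | 0.496 |
| Wald, upper limit cut at 1 | 0.371 | 0.286 | 0.448 |
| Wilson | 0.423 | 0.386 | 0.453 |
| Jeffreys | 0.420 | 0.370 | 0.459 |
| Agresti-Coull, untruncated | 0.455 | 0.430 | 0.475 |
| Mid-P | whole counts only | 0.399 | 0.485 |

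The untruncated Wald width at 85% is 2 × 1.96 × √(0.85 × 0.15 / 10) = 0.443. No method in the table stays within 0.40 at 8/10.

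**Does 'about 10' leave room?** The expected exact width at p = 0.85 is 0.412 for n = 13, 0.398 for n = 14 and 0.385 for n = 15. Even then 0.40 is not a limit: P(width ≤ 0.40) is 36% at n = 14 and 60% at n = 15. The exact width interpolated at 85% is 0.402 at n = 15 and first falls below 0.40 at n = 16 (0.389).

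**The case against.** The best defence is that this is a small descriptive pilot. Section 7.3 says it studies feasibility rather than efficacy or futility, no test or stopping rule uses the 0.40, and the interval eventually reported will be correct whatever 7.1 says. That stands, and it limits the consequence: the design and analysis need no change. It does not make the sentence true, because 7.1 uses local control precision, and nothing else, to support the number of patients.

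A second defence is that the figure may come from a different method. A Wald interval at 85% with its impossible upper limit of 1.071 cut to 1 has width 0.371, which satisfies the bound. Wilson, Jeffreys and mid-P also do so at 9/10. So the figure does not fail under every method, and that should be conceded. However, the truncated Wald origin is only an inference. Section 7.2 commits to the exact method, and every method in the table exceeds 0.40 at 8/10.

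Third, 0.44 to 0.53 is not the whole range of outcomes. Results of 8 or 9 of 10 have a combined probability of 0.276 + 0.347 = 62% at a true rate of 85%; 10/10 would be narrower and 7/10 wider. This is correct, and the range should be tied to those two counts.

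Finally, up to 15 patients may be enrolled. But 15 is a ceiling for reaching ten completers, and those who do not complete are left out of the analysis, so 15 is not the planned number analysed.

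**Conclusion.** The concern holds. Under the plan's own assumptions (10 patients analysed, true local control 85%, exact binomial 95% interval), the width is 0.44 at 9/10 and 0.53 at 8/10, with an expected value of 0.47. The stated limit of 0.40 is met about one time in five, in effect only if all 10 patients are controlled. The 47% is correct division of a wrong input.

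The error overstates the precision of a primary estimate. It does not invalidate the pilot or change how local control will be analysed.

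**What to change.** Replace the precision sentence in Section 7.1, keeping to the planned number analysed. For example:

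> With 10 evaluable patients, the exact (Clopper-Pearson) 95% confidence interval for local control would be 44% to 97% if 8 are controlled, 55% to 99.7% if 9 are controlled, and 69% to 100% if all 10 are controlled (widths 0.53, 0.44 and 0.31). If the true rate is 85%, the expected width is 0.47.

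Remove the 0.40 limit and the 47% that follows from it. Do not quote the precision for 15 evaluable patients, since that is not the planned case. If the sponsor did mean a different interval, Sections 7.1 and 7.2 should name the same one, but a limit of 0.40 would still fail at 8/10 for every method tabulated above.

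The cost is one reworded sentence and a less favourable stated precision. It needs no extra patients and no change to the analysis.

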## **7.2 Methodology of comparisons between groups**

Descriptive statistics, including means, medians, and ranges will be reported wherever appropriate. For the primary hypothesis, the estimated rates of local control and its 95% confidence interval using an exact binomial method will be computed. For the secondary objectives, appropriate Kaplan Meier progression-free survival estimates will be computed.

All calculations will be performed using the SAS and the R language for statistical computing. Unless explicitly mentioned, all analysis will use a type I error rate of 0.05 and 95% confidence intervals.

## **7.3 Missing data and interim stopping**

If patients do not complete the follow-up period, patients will be considered lost to attrition and their data will not be used for the primary or secondary objectives, except possibly for demographic descriptions. No missing data imputation or specific analysis is planned for this study. Since the primary objectives of this study are to study feasibility rather than evaluate efficacy or futility – early stopping is not meaningful in the present context. No stopping rules or interim evaluations are planned for this study.

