## STUDY SCHEMA

## STUDY CALENDAR

Procedure	Screening 	Radiosurgery Delivery	Surgical Resection	Post-Surgical Resection Visit	Follow-up  (until 18-months from post-surgical resection visit) (18 months)
Study Day/Visit Day	Day – 30 to Enrollment	Day 1	Day 2 (+8 days)	1-month ±7 days from radiosurgery	Every 3 months ±14 days
Informed Consent	X				
AE Reporting	X	X	X	X	
Concomitant Medications	X	X	X	X	X
SRS		X		X	
Physical Exam 	X			X	X
Medical History	X				
ECOG Performance Status	X			X	X
Pregnancy Test (Serum or Urine) 	X				
Neurocognitive Testing 	X				
QOL Questionnaire 	X			X	X
MRI (Brain) 	X			X	X

1. All screening procedures must occur within 30 days prior to enrollment. Treatment must start within 14 days of enrollment.
2. If a subject has disease progression/relapse or subject withdrawal, then they will be followed as per follow-up requirements.
3. Including height and weight on screening. Temperature, HR, RR, BP and O2 sats or as per institutional standards at all timepoints.
4. For women of childbearing potential, a negative pregnancy test (serum or urine) must be obtained within 30 days prior to the first study intervention.
5. Neurocognitive testing: Multilingual Aphasia Examination Controlled Oral Word Associated Test (COWAT), Trail Making Test, Parts A and B (TMT), and Hopkins Verbal Learning Test-Revised (HVLT-R).
6. QOL Questionnaire: MDASI-BT, EQ-5D-5L.
7. MRI (brain) w/ contrast. Radiographic assessments will be completed as per RANO criteria (see Appendix 3).

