## **2.2 Secondary Objective(s)**

1. To assess survival (CNS progression-free survival and overall survival) for patients undergoing preoperative SRS and surgical resection.
2. To document rates of leptomeningeal carcinomatosis for patients undergoing preoperative SRS and surgical resection.
3. To record incidence of radiation necrosis in patients undergoing preoperative GK-SRS and surgical resection.
4. To document quality of life measures using preoperative GK-SRS and to compare to historically cited rates using postoperative GK-SRS.

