## **2.3 Primary Endpoint**

1. Feasibility for this study will be defined as 50% of enrolled study subjects undergoing the surgical resection as per the protocol.
2. Measure rate of local control at the resection cavity any new tumors by post-treatment MRI.

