## **2.4 Secondary Endpoint(s)**

1. CNS progression-free survival and overall survival will be evaluated at six, 12, and 18 months following surgical resection.
2. Rates of leptomeningeal carcinomatosis using preoperative GK-SRS will be documented and compared to historically cited rates for postoperative GK-SRS.
3. Incidence of radiation necrosis will be measured by post-treatment MRI.
4. Quality of life measures will be collected and will be compared to historically cited data.

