## **3.2 Design of the Current Study**

Enrolled patients will receive GK-SRS to all metastases followed by surgical resection of resectable metastases within one to 10 days following GK-SRS. Pathologic specimens will be analyzed, and the patient will enter a standard pattern of surveillance (brain MRI every three months for two years).

Quality of life will be assessed every three months, and neurocognitive evaluations will be performed every six months. These parameters will be compared to baseline testing performed at the time of enrollment. Local control, CNS progression-free survival, overall survival, rates of leptomeningeal carcinomatosis, rates of radiation necrosis, and steroid requirements will also be documented and compared with historically reported rates.

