## **4.7 Lost to Follow-up**

The following actions must be taken if a participant fails to return to the clinic for a required study visit and/or is unable to be reached for follow-up:

- The investigator or designee must make every effort to regain contact and/or reschedule a missed visit with the participant.
- A participant is deemed lost to follow-up if his/her status cannot be obtained after *all* of the following occurs at two consecutive scheduled protocol calendar timepoints:
  - Three telephone calls (at least one day apart) from the study team are unanswered  

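### Section 7.3 drops every patient who does not complete follow-up, which contradicts the enrolled denominator for feasibility, the survival landmarks and Kaplan-Meier censoring

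*Combined protocol and SAP*

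**What the plan says.** Section 7.3 sets one rule for incomplete follow-up: "patients will be considered lost to attrition and their data will not be used for the primary or secondary objectives". The only carve-out is a possible one for demographics. No imputation or other missing-data analysis is planned.

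The rule meets these parts of the plan:

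- **Feasibility (2.3):** "Feasibility for this study will be defined as 50% of enrolled study subjects undergoing the surgical resection as per the protocol". Resection is scheduled one to 10 days after radiosurgery (3.2).
- **Survival (2.4):** "CNS progression-free survival and overall survival will be evaluated at six, 12, and 18 months following surgical resection". The objective in 2.2 covers all patients who have radiosurgery and resection.
- **Method (7.2):** "For the secondary objectives, appropriate Kaplan Meier progression-free survival estimates will be computed". No censoring rule is written, and no method is named for OS.
- **Length of follow-up:** the Study Calendar runs "until 18-months from post-surgical resection visit", while 3.2 and the Protocol Summary describe "brain MRI every three months for two years".
- **Who has left:** 4.7 defines loss to follow-up by failed contact at two consecutive timepoints. Section 4.9 treats a discontinued participant as having completed the study, without mentioning death or loss to follow-up. Section 7.3 speaks of attrition, does not define it, and refers to neither section.
- **Progression:** calendar note 2 keeps progressed or withdrawn subjects in follow-up, and 4.6 does the same after treatment discontinuation. The investigator-withdrawal text in 4.6 lists progression as a reason for withdrawal.
- **Numbers (Protocol Summary):** up to 15 enrolled to obtain ten completed.

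**The concern.** The rule selects the analysis set on something that happens after the outcome, or that is the outcome. Whether a patient was resected is known within about 10 days of radiosurgery, but a withdrawal a year later would remove that patient from the feasibility calculation. Death ends follow-up, so the rule may also delete the events that OS and CNS progression-free survival (PFS) are meant to count. Because the plan does not say whether death is attrition, two analysts following it faithfully could report opposite biases.

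At stake are the feasibility verdict, which 7.1 calls the primary objective, and the survival estimates that 3.2 intends to compare with historical rates. Local control, leptomeningeal disease and necrosis are affected too, but the documents do not allow the direction or size of that bias to be determined.

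**Working it through.** The plan gives no figure for the effect of this rule, so there is none to reproduce.

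**1. Feasibility.** Inputs: up to 15 enrolled (Protocol Summary) and the 50% criterion (2.3), read as at least 50%.

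| All enrolled | Dropped under 7.3 | Rate after dropping |
|---|---|---|
| 7/15 = 46.7%, fails | 1 unresected | 7/14 = 50.0%, passes |
| 7/15 = 46.7%, fails | all 8 unresected | 7/7 = 100%, passes |
| 8/15 = 53.3%, passes | 2 resected | 6/13 = 46.2%, fails |
| 7/14 = 50.0%, passes | 1 resected | 6/13 = 46.2%, fails |

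**2. OS if death counts as not completing.** Every patient kept is alive at the end of follow-up, so OS is 100% at 6, 12 and 18 months whatever the true survival. The documents give no survival curve, only an eligibility floor of a six-month estimated median (inclusion criterion 8). Assume exponential survival, S(t) = 0.5^(t/median). The share alive at 18 months, and the expected number of 15, are:

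- median 6 months: 12.5%, 1.9 patients
- median 12 months: 35.4%, 5.3 patients
- median 24 months: 59.5%, 8.9 patients

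With a 12-month median, 35% would be kept under an 18-month period and 0.5^2 = 25% under 24 months.

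**3. OS if only dropouts are removed.** Deaths stay, while event-free time from dropouts is discarded. Let μ = ln 2/median, F = 18 months, and ν = −ln(1 − d)/18 for an assumed independent dropout proportion d. A patient is kept unless dropout comes before both death and F. Define G(x) = 1 − [ν/(μ+ν)]·[1 − exp(−(μ+ν)(F − x))]. Then

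S_kept(t) = exp(−(μ+ν)t)·G(t)/G(0).

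For a 12-month median and d = 0.20, μ = 0.0578, ν = 0.0124 and G(0) = 0.873, so 87% of patients are kept.

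| Month | True OS | OS among those kept |
|---|---|---|
| 6 | 70.7% | 0.590/0.873 = 67.6% |
| 12 | 50.0% | 0.405/0.873 = 46.3% |
| 18 | 35.4% | 0.283/0.873 = 32.4% |

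Range at 12 months, with a 12-month median: d = 0.10 gives 48.3% and d = 0.30 gives 44.2%. With d = 0.20 and medians of 6, 12, 18 and 24 months, true values of 25.0%, 50.0%, 63.0% and 70.7% become 22.4%, 46.3%, 59.5% and 67.6%.

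**4. Kaplan-Meier on an invented ten-patient set.** Deaths at 4, 7, 10, 13 and 16 months; lost at 8 and 14; three followed to 18.

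- All kept, with censoring: 6 months, 9/10 = 0.90; 12 months, 0.90 × 8/9 × 6/7 = 0.69; 18 months, that product × 5/6 × 3/4 = 0.43.
- Only the two lost patients removed: 7/8 = 0.875, 5/8 = 0.625, 3/8 = 0.375.
- Only the three 18-month completers kept: 1.00 at each landmark.

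**The case against.** The strongest reply is that nobody would read 7.3 so as to delete deaths. Landmark OS in 2.4 would be empty, and 4.6, 4.9 and calendar note 2 lean towards keeping patients who progress or discontinue. That makes the dropout-only reading the more natural one, and 100% OS should be seen as the extreme. But none of those passages covers loss to follow-up or restores deleted data, and the natural reading is still biased.

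That bias is modest for this trial. A fall from 50% to 46% is small beside a binomial standard error of √(0.25/10) = 16 points with ten patients or √(0.25/15) = 13 points with 15, and no decision rule hangs on OS or PFS. This stands: the weight of the point rests mainly on feasibility.

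On feasibility, it can be said that 2.3 names its own denominator and should prevail, and that the flips are edge cases. If *completed* includes resection and ten complete, at least 10/15 = 67% are resected and dropping non-completers cannot produce a failure. So the flips need the ten-completer target to be missed. However, the plan does not define *completed* that way or say that 2.3 overrides 7.3. If death counts as not completing and median survival is 12 months, the chance that at least ten of 15 reach 18 months is only about 1.35% (39% with a 24-month median).

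Three smaller points also stand. Kaplan-Meier is named only for PFS and no censoring rule is written, so the conflict is with the method's normal use. Two years of routine imaging can coexist with 18 months of study follow-up, so that difference may be one of wording. And the calendar counts from a visit about one month after radiosurgery, so the 35% kept would be about 33% at 19 months.

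**Conclusion.** The concern holds. As written, 7.3 conflicts with the enrolled denominator in 2.3, with the landmarks in 2.4 and with normal Kaplan-Meier practice under 7.2, and nothing elsewhere repairs it. This is an operative rule that gives wrong results if followed, so it must be fixed before analysis.

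One or two deletions can reverse the feasibility verdict in either direction. That result rests on reading the criterion as at least 50% and on totals close to it. OS is either 100% by construction or understated, by about 3 to 4 points under the central assumptions (exponential survival, 12-month median, 20% independent dropout). CNS PFS is exposed to the same two biases, but its size was not calculated.

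**What to change.** Replace the exclusion sentence in 7.3 with text to this effect:

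> Feasibility is analysed in all enrolled subjects; a subject not resected per protocol for any reason counts as not feasible. OS, CNS PFS, local control, leptomeningeal disease and necrosis are analysed in all subjects who received SRS and resection, from the date of resection, whether or not they complete follow-up. OS and CNS PFS are estimated by Kaplan-Meier; death is an event for both, and other subjects are censored at last contact (OS) or last brain MRI (CNS PFS). Local failure, leptomeningeal disease or necrosis observed before death or withdrawal is counted. Quality of life is summarised at each visit from all available questionnaires. Subjects given SRS but not resected are listed separately.

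In addition:

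- In 7.2, state the landmark for the exact binomial local-control rate and how death or loss before it is treated. For local control, leptomeningeal disease and necrosis, report the counts with the event, event-free at the landmark, dead without the event and lost without the event.
- State that 4.9 does not define the analysis set, and define *completed* for the ten-subject target.
- Reconcile the follow-up length in the calendar with the Protocol Summary and 3.2, and reconcile calendar note 2 with the two parts of 4.6 on whether subjects who progress stay in follow-up.

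The cost is wording in 7.2, 7.3 and 4.9, reconciling lines elsewhere and slightly more analysis. No new patients or data are needed, provided the follow-up length is reconciled without adding visits. Reported feasibility or OS may look less favourable.

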## **4.6 Discontinuation of Study Treatment, Withdrawal, and Compliance**

Discontinuation from the study treatment does not mean discontinuation from the study. Subject will be considered in follow-up; study procedures should still be completed as indicated by the study protocol and AEs/SAEs will continue to be reported according to this protocol.

In the absence of treatment delays due to adverse events, study treatment/intervention may continue until:

- Disease progression.
- General or specific changes in the subject's condition renders the subject unacceptable for further treatment in the investigator's judgment.
- Intercurrent illness that prevents further treatment administration.
- Subject decides to withdraw from the study.
- The subject has significant noncompliance with the protocol (see below).
- Unacceptable adverse event(s) and/or dose level reduction beyond requirements as detailed in this protocol.
- Study stopping rules are met.

Subjects who sign the informed consent form, and are enrolled and receive the study intervention, but subsequently withdraw, or are withdrawn or discontinued from the study will not be replaced.

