### **Consent Withdrawal**

A subject may decide to withdraw from the study at any time. MCWCC CTO will follow its IRB of record's SOPs regarding consent withdrawal.

If a subject intends on withdrawing consent, staff should confirm which of the following options the subject chooses and document the discussion:

- Full consent withdrawal with no study follow-up.
- Selective consent withdrawal from interventional portion of the study but agree to continued follow-up of associated clinical outcome information.

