### **Investigator-initiated Withdrawal**

The investigator will withdraw a subject whenever continued participation is no longer in the subject's best interests. Reasons for withdrawing a subject include, but are not limited to, disease progression, the occurrence of an adverse event or a concurrent illness, a subject's request to end participation, a subject's noncompliance or simply significant uncertainty on the part of the investigator that continued participation is prudent. The reason for study withdrawal and the date the subject was removed from the study must be documented.

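### Section 7.3 removes every patient who does not finish follow-up from all primary and secondary objectives, even after death or a recorded recurrence, and local control has no time point

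*Combined protocol and SAP*

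**What the plan says.** Section 7.3 sets one rule for incomplete follow-up: "patients will be considered lost to attrition and their data will not be used for the primary or secondary objectives". The only use it leaves open for these patients is demographic description. It plans no imputation or other missing-data analysis, and mentions neither death, nor an event recorded before loss, nor censoring.

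Section 7.2 plans, for local control, that "the estimated rates of local control and its 95% confidence interval using an exact binomial method will be computed", and for the secondary objectives that "appropriate Kaplan Meier progression-free survival estimates will be computed". Section 2.3 defines feasibility as a proportion of enrolled subjects. Section 2.4 sets landmarks of 6, 12 and 18 months for CNS progression-free survival and overall survival. No horizon for local control appears in the Protocol Summary or in Sections 2.1, 2.3, 7.1 or 7.2. Section 3.2 plans to compare it with historical rates.

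Several places bear on who completes follow-up:
- Section 4.6: "Discontinuation from the study treatment does not mean discontinuation from the study. Subject will be considered in follow-up".
- Study Calendar, footnote 2: "If a subject has disease progression/relapse or subject withdrawal, then they will be followed as per follow-up requirements".
- Consent Withdrawal (4.6) allows "Full consent withdrawal with no study follow-up", and also selective withdrawal with outcome follow-up continuing.
- Investigator-initiated Withdrawal (4.6): "Reasons for withdrawing a subject include, but are not limited to, disease progression".
- Section 4.9 counts a discontinued participant as having completed the study.
- The calendar's follow-up runs "until 18-months from post-surgical resection visit", while the Protocol Summary and Section 3.2 describe two years of three-monthly brain MRI.

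**The concern.** Death before the end of follow-up is to be expected in this population: eligibility requires only an estimated median survival of at least six months. A rule that keeps completers alone selects patients on the outcome being measured when that outcome is survival. For local control it discards usable scans and can discard failures that have been observed. With about ten patients, moving one or two of them changes the headline result. A local control rate without a horizon cannot be interpreted or set beside a historical figure, and here the horizon would be whatever the completers' follow-up happens to be, which the documents give in two lengths.

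**Working it through.** **1. Survival endpoints.** Completing follow-up requires being alive at its end, about 18 months after resection on the calendar and later on the two-year text. Every patient analysed is therefore alive at 6, 12 and 18 months, and overall survival is 100% at each landmark whatever the true survival. This needs no assumption about prognosis. For CNS progression-free survival, no death can enter as an event and no early departure as a censored observation. Only progressions in patients who then survive to the end remain. Kaplan-Meier estimation is designed to use what has been discarded.

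**2. Feasibility.** Section 2.3 uses all enrolled subjects as the denominator. Section 7.3 covers all primary objectives, so it removes enrolled subjects from that denominator. Both cannot be followed.

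**3. Patients left for local control.** The documents give no survival curve. Assume exponential survival, S(t) = 0.5^(t/median), with cohort medians of 6, 12 and 18 months. The 6-month value takes the per-patient eligibility floor as the cohort median, so it is a worst case.

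| Median (months) | Alive at 18 months | Of 10 | Alive at 24 months | Of 10 |
|---|---|---|---|---|
| 6 | 0.125 | 1.25 | 0.0625 | 0.6 |
| 12 | 0.354 | 3.5 | 0.250 | 2.5 |
| 18 | 0.500 | 5.0 | 0.397 | 4.0 |

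These are upper limits on completers under each assumption, since withdrawals come off as well.

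**4. Recorded recurrences.** Take ten resected patients: eight complete with control, and two have a recorded local recurrence and then die or leave. Exact (Clopper-Pearson) 95% intervals:
- Under 7.3: 8/8 = 100%, lower limit 0.025^(1/8) = 0.631, so 63-100%.
- With the recorded failures counted: 8/10 = 80%, 0.444 to 0.975, so 44-97%.

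This is the extreme case, in which every lost patient had recurred.

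**5. Is local control overstated in general?** Assume 85% control at 12 months (Section 7.1 gives 85% without a horizon), constant hazards L = -ln(0.85)/12 and M = ln 2/median, and a death hazard that doubles after local failure. At 18 months:
- Control ignoring death: 0.85^1.5 = 78.4%.
- Completers: a/(a+b), with a = exp(-18(L+M)) and b = L·exp(-36M)·(exp(18(M-L))-1)/(M-L). This gives 90.0%, 85.6% and 83.6% for medians 6, 12 and 18.
- One minus the cumulative incidence of local failure with death competing: 1 - [L/(L+M)]·(1-exp(-18(L+M))) = 90.5%, 86.3% and 84.2%.

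Completers read higher than the first quantity and are within one percentage point of the second, slightly below it. If recurrence does not affect death, completers show 78.4%, equal to the first quantity and below the second. The direction therefore depends on the estimand.

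**6. The horizon.** Under the same constant hazard, 85% at 12 months corresponds to 0.85^0.5 = 92.2% at 6 months, 78.4% at 18 and 0.85^2 = 72.2% at 24.

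**The case against.** The strongest reply is that nobody would apply 7.3 to deaths. Attrition can mean dropout, Section 4.9 treats a discontinued participant as having completed the study, and survival landmarks make sense only if deaths are kept. That may be the intention, but 7.3 depends on completing the follow-up period, which is a different term from the one in 4.9, and it makes no exception for death. Section 4.9 is a further passage to reconcile and does not resolve the problem.

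A second reply is that patients who recur stay in follow-up. This is largely right. Section 4.6, calendar footnote 2 and the selective-withdrawal option all provide for it, so a reader should not infer that recurrence by itself removes a patient. The loss affects those who recur and then die, withdraw fully or are withdrawn by the investigator, for which progression is a listed reason.

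Third, this is a small pilot that puts feasibility first and sets no decision threshold on local control. That limits the stakes, but local control is a named primary objective and the hypothesis in Section 2 is about it.

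A reader might also infer that ten completed subjects out of at most fifteen (10/15 = 67%) is unattainable against the 12% to 50% above. That depends on whether completed has the 7.3 meaning, which the documents leave open, and on assumed medians.

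**Conclusion.** The concern holds. As written, 7.3 makes overall survival uninformative, removes deaths and censored follow-up from CNS progression-free survival, and contradicts the feasibility denominator. These conclusions follow from the text alone. For local control the supported claims are a smaller sample, with about 12% to 50% of patients alive at 18 months under the assumed medians, and the loss of recorded failures in patients who later die or leave. The shift from 80% to 100% shows what is possible and does not forecast what will happen.

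A reader might infer that the rule generally inflates local control. The documents do not support that: the comparison depends on whether the target ignores death or treats it as competing, and on an unstated link between recurrence and loss. The missing time point is a separate and certain omission. It matters because the planned historical comparison needs a horizon, and the only dated postoperative local control figure in the documents (Section 1.6) is at 24 months, beyond the calendar's 18.

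**What to change.** 1. Delete the exclusion in 7.3. Compute feasibility on all enrolled subjects. For overall survival and CNS progression-free survival, count deaths as events and censor others at last contact or last MRI respectively. Always count a recorded local recurrence as a failure.
2. State a time point for local control at the resection cavity, with one outcome per patient. An existing landmark such as 12 months after resection would serve.
3. In all resected patients, estimate the cumulative incidence of local failure at that time, with death without local failure as a competing event. Keep the exact binomial interval, with all resected patients as denominator and local failure recorded by the time point as the event, and report how many died or were lost without failure. The exact interval is worth keeping because, at 85% control and n = 10, the chance of no failures is 0.85^10 = 0.197; the usual time-to-event interval then has zero width, while the exact interval for 10/10 is 69-100%. Patients lost alive count as non-failures in this binomial, so their number must be shown. Do not restrict it to patients with known status: that keeps failures in patients who later die and drops those who die controlled. Under the assumptions in step 5 of the working it would read 72%, 80% and 82% at 12 months for medians 6, 12 and 18, against 85% ignoring death and 92%, 89% and 88% with death competing.
4. Label the historical comparison of local control as descriptive unless the horizons match. A 12-month endpoint has no dated postoperative counterpart in the documents.
5. Reconcile the 18-month calendar with the two-year MRI surveillance in the Protocol Summary and Section 3.2, and the wording of 4.9 with 7.3.

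The cost is wording in the Protocol Summary, the calendar and Sections 2.3, 3.2, 4.9, 7.2 and 7.3, plus a few lines of code. The three-monthly MRIs are already scheduled. The downside is slightly more analysis work and an interval that stays wide.
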